Time to event data (for example, time to clinical remission) will be analyzed by Kaplan-Meier analysis (PROC LIEFTTEST in SAS/STAT) stratified by country. Additionally, the change from baseline in continuous outcomes measured at multiple post-baseline time points will be analyzed longitudinally using a mixed model. Models will include fixed effects for baseline

value, country, treatment, week and the treatment by week interaction and allow for random subject effects. Treatment and week will each be fit as categorical variables. Models will be fit using SAS Proc Mixed assuming a compound symmetric correlation structure allowing for heterogeneous variances by week. The Kenward-Rogers approach for computing denominator degrees of freedom will be used to account appropriately for pooling of within-and between-subject variance estimates. Least squares means with 95% confidence intervals will be presented for each treatment*week cross-classification. The basic SAS code will follow the structure below:

proc mixed;

class treatment country week subjectID;
model Y = baseline country treatment week treatment*week/ddfm=KenwardRoger solution;
random int/ subject=subjectID type =VC;
lsmeans treatment*week/stderr;
run;

Estimate and contrast statements will be included to compare the mean change from baseline averaged over all weeks for the treatment comparison.

To determine whether the declaration of response based on the co-primary endpoints for induction parallels the pattern of CDAI scores, Spearman correlation analyses will be applied to CDAI scores with the occurrence or non-occurrence of response based on the co-primary endpoints (Yes or No). Wilcoxon rank-sum test will be conducted to compare changes in the CDAI scores between responders and non-responders to the co-primary endpoints.

The Work Productivity and Activity Impairment Questionnaire: Crohn's disease (WPAI: CD) is an instrument with 6 questions that will be used to assess the effect of CD on subjects' work habits. A copy of the WPAI: CD questionnaire is provided in Appendix 6.

WPAI: CD outcomes are expressed as impairment percentages, with higher numbers indicating greater impairment and less productivity, i.e., worse outcomes. The four WPAI: CD outcome scores are computed as follows:

- % work time missed due to CD = 100*Q2/(Q2+Q4)
- % impairment while working due to CD = 100*Q5/10
- % overall work impairment= 100*[Q2/(Q2+Q4)+[(1-Q2/(Q2+Q4)]*(Q5/10)]
- % activity impairment due to CD = 100*Q6/10

The IBDQ Global Score is the sum of 32 responses, each ranging from 1 to 7, thus the Global Score ranges from 32 to 224; a higher score indicating a better quality of life. A copy of the IBDQ questionnaire is provided in Appendix 5.

Changes from baseline in the four WPAI: CD and IBDQ Global Score outcomes will be analyzed by the methods outlined above for continuous outcomes.

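### Section 8.6.2 describes a separate variance for each week in the longitudinal mixed model, but its SAS code fits one variance common to all weeks

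*Protocol*

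**What the plan says.** Protocol section 8.6.2 adds a longitudinal mixed model for change from baseline in continuous outcomes with several post-baseline visits. The model is to "allow for random subject effects". Its covariance is described as follows: "Models will be fit using SAS Proc Mixed assuming a compound symmetric correlation structure allowing for heterogeneous variances by week". The promised output is: "Least squares means with 95% confidence intervals will be presented for each treatment*week cross-classification".

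The section then states "The basic SAS code will follow the structure below" and prints these lines, among others:

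- "class treatment country week subjectID"
- "model Y = baseline country treatment week treatment*week/ddfm=KenwardRoger solution"
- "random int/ subject=subjectID type =VC"
- "lsmeans treatment*week/stderr"

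The code has no REPEATED statement and no GROUP= option. The only additions the section names are ESTIMATE and CONTRAST statements for the treatment comparison averaged over all weeks.

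**The concern.** The sentence asks for one common correlation and a separate variance at each week (heterogeneous compound symmetry). The code is a plain random-intercept model (homogeneous compound symmetry). ESTIMATE and CONTRAST statements do not alter the covariance, so nothing that the section says will be added closes the gap, and no other section says whether text or code takes precedence.

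The treatment-by-week intervals depend directly on the weekly variance, so they are what is at stake. The outcomes concerned are:

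- IBDQ and WPAI:CD change, at Weeks 16, 28, 40 and 52;
- inflammatory markers, including fecal calprotectin, and SES-CD change, at Weeks 16 and 52.

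**Working it through.** **1. Covariance implied by each specification (T visits)**

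| | Variance at week t | Covariance, weeks j and k | Parameters, T = 4 | Parameters, T = 2 |
|---|---|---|---|---|
| Text | σ_t², one per week | ρσ_jσ_k | 5 | 3 |
| Code | σ_b² + σ_e², same every week | σ_b² | 2 | 2 |

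The VC type applies to the single random intercept, and the residual keeps one variance. The fixed effects and the Kenward-Roger option agree between text and code, so the conflict is confined to the covariance.

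**2. Check by fitting.** The code's model was fitted by REML to one simulated complete data set with 330 per arm, four visits, assumed SDs of 25, 30, 35 and 40, and correlation 0.5. The standard error of the treatment difference came out as 2.55 at all four weeks. The true values are 1.95, 2.34, 2.72 and 3.11.

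**3. Formula for the promised intervals.** The plan gives no figure to reproduce. It supplies N = 660 and country as a fixed class effect. Weekly SDs, correlation and country sizes are assumed. Complete data and equal arms within country are also assumed. With equally weighted LS means over countries:

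- true variance of an LS mean at week t = SD_t²/(N/2) + v(F−1)/N;
- v = (sum of all entries of the weekly covariance matrix)/T²;
- F = arithmetic mean/harmonic mean of the country sizes, with F = 1 when they are equal.

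The code replaces SD_t² with the mean of the weekly variances and estimates the second term correctly. Hence:

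- SE ratio (code/true) = √{[2·mean(SD²) + v(F−1)] / [2·SD_t² + v(F−1)]};
- coverage = 2Φ(1.96 × ratio) − 1.

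**4. Worked case: SDs 1, 1.2, 1.35, 1.5; correlation 0.5**

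- mean(SD²) = (1 + 1.44 + 1.8225 + 2.25)/4 = 1.628.
- v = (0.5 × 5.05² + 0.5 × 6.5125)/16 = 1.000.
- Equal countries (F = 1): first visit √1.628/1 = 1.276, coverage 98.8%; last visit 1.276/1.5 = 0.851, coverage 90.5%.
- 15 uneven countries (200, 140, 90, 60, 44, 32, 24, 18, 14, 10, 8, 6, 6, 4, 4; F = 3.87): first visit √[(3.256 + 2.87)/(2 + 2.87)] = 1.121, coverage 97.2%; last visit √[(3.256 + 2.87)/(4.5 + 2.87)] = 0.912, coverage 92.6%.

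**5. Range over assumptions (coverage at first/last visit)**

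| Assumed SD pattern | Equal countries | 15 uneven |
|---|---|---|
| Four visits, rising to 1.5 times | 98.8% / 90.5% | 97.2% / 92.6% |
| Four visits, rising to 1.3 times in equal steps | 97.6% / 91.8% | 96.5% / 93.4% |
| Four visits, rising to 1.1 times in equal steps | 96.1% / 93.9% | 95.6% / 94.4% |
| Two visits, ratio 1.5 | 98.8% / 90.4% | 97.0% / 92.8% |
| Equal SDs | 95% / 95% | 95% / 95% |

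Other country patterns for the 1.5-fold rise:

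- 10 mildly uneven, sizes 30 to 120 (F = 1.24): 98.6% / 90.8%;
- 10 uneven, sizes 6 to 250 (F = 3.90): 97.2% / 92.6%;
- 20 uneven, sizes 2 to 200 (F = 5.45): 96.8% / 93.1%.

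With 15 uneven countries, moving the correlation from 0.3 to 0.7 changes the result only from 97.5% / 92.3% to 97.0% / 92.9%. If SDs fall over time, the two figures swap.

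**6. Simulation check.** With country and a baseline covariate in the model, 8,000 replicates and SDs rising to 1.5 times, coverage was 98.7% / 90.4% (equal) and 97.2% / 92.9% (15 uneven). This agrees with the formula.

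**7. All-weeks contrast.** With complete data the random-intercept fit reproduces v exactly, because it matches the mean variance and the mean covariance. The SE ratio is therefore 1.00, and the simulated size was between 4.9% and 5.1%.

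**The case against.** The strongest reply is that the prose specifies the model and the code is only a sketch. The section calls the code basic, and it is incomplete elsewhere: it requests standard errors but omits the option that prints the promised confidence limits. Section 8.0 leaves computational detail to a statistical analysis plan to be finalised before database lock. If the text governs, no interval is miscalibrated and only a code line needs correcting.

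That last statement is right, and it limits the severity. It does not remove the conflict. The missing confidence-limit option changes only what is printed, whereas the RANDOM line is a complete covariance specification that differs from the text. Detail left to the analysis plan would be no finding, but here the protocol itself fixes two models, and whoever writes that plan must depart from one of them.

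Several further points stand:

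- Every SD, correlation and country size above is assumed. The calculations also assume complete data, although section 8.2 allows 20% for drop-out. The coverages are not a forecast for this trial.
- The only comparison named for this model is the all-weeks contrast, which is unaffected with complete data. No week-specific treatment test from it is named.
- Section 8.6.2 also gives a separate fixed-effects model for change from baseline.
- Heterogeneous compound symmetry still assumes one constant correlation between visits up to 36 weeks apart, which the protocol does not support with data.

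**Conclusion.** The concern holds. The text and the code of section 8.6.2 specify incompatible covariance models, and the protocol does not say which to use. This follows from the wording and needs no assumption.

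The consequence is conditional: it arises only if the code is run as printed and the weekly SDs differ. A week at the average variance keeps 95% coverage. In the illustrations, first- and last-visit coverage ranges from 95.6% and 94.4% (1.1-fold rise, 15 uneven countries) to 98.8% and 90.5% (1.5-fold rise, equal countries). The CMH tests of the co-primary and key co-secondary endpoints are untouched. Severity is minor.

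**What to change.** Make the code match the text. Replace the RANDOM line with `repeated week / subject=subjectID type=csh;` and state that the common within-subject correlation represents the random subject effects named in the text. Keeping the RANDOM line and adding separate residual variances by week would not do: that gives a constant covariance, not the constant correlation the text names.

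If a single common variance is intended, delete the clause on heterogeneous variances and keep the code. The first repair is preferable because its variance model holds whether or not the SDs differ, although it keeps the constant-correlation assumption already in the text. Adding `cl` to the LSMEANS line is optional housekeeping. The choice should be settled before unblinding.

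The cost is one code line and one sentence, with no extra data. Covariance parameters rise from 2 to 5 with four visits and from 2 to 3 with two, which is small against 660 planned subjects. The work-related WPAI:CD scores rest on fewer subjects (number not given), because Appendix 6 sends those not in paid work straight to question 6.

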- Endoscopic remission defined as a SES-CD score of ≤ 2 at Week 52. SES-CD scores will be calculated from centrally-read digital video of ileocolonoscopies performed at Week 52.

In the Phase 3 studies Salix is conducting, these endpoints will be evaluated for responsiveness (i.e., demonstrate the ability to detect clinically meaningful change in disease activity indexes of CD, for example full CDAI) and validity (i.e., demonstrate correlations

Confidential

with other measures of disease activity indexes of CD). These attributes are consistent with recommendations in the published FDA Guidance for Industry on the use of patient-reported outcomes (2009) (38).

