2.2 Endpoints

2.2.1 Primary Efficacy Endpoints

There will be two co-primary measures of efficacy for Induction of Clinical Remission and Endoscopic Response. The first co-primary endpoint is:

 Clinical symptom remission defined by (1) the total number of liquid/very soft stools for the 7 days prior to the Week 16 visit being ≤ 10 (from CDAI Item 1); AND (2) an abdominal pain rating of ≤ 1(from CDAI Item 2) on each day for the 7 days prior to the Week 16 visit.

The second co-primary endpoint is:

 Endoscopic response defined as a ≥ 3-point decrease in the SES-CD from baseline to the SES-CD score obtained between Week 16 and Week 17. SES-CD scores will be calculated from centrally-read digital video of ileocolonoscopies performed at baseline and between Week 16 and Week 17.

Confidential

For the daily stool data, the number of daily liquid/very soft stools with a consistency of a Bristol Stool Form Scale [BSFS] score of Type 6 or Type 7 will be assessed using the information recorded by the subject via an electronic diary system. The number of liquid/very soft stools in a given week will be calculated as follows:

(Number of liquid/very soft stools during that week ÷ Number of days with nonmissing assessments during that week) × 7

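### For symptom remission, the planned comparison with total CDAI is part-whole, so its significance test cannot count as evidence of validity

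*Protocol*

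**What the plan says.** Section 2.2.1 defines the symptom co-primary from two CDAI diary items. One is a 7-day total of at most 10 liquid or very soft stools (Item 1). The pain half reads: "AND (2) an abdominal pain rating of ≤ 1(from CDAI Item 2) on each day for the 7 days prior to the Week 16 visit". A separate rule gives the other co-primary: "Endoscopic response defined as a ≥ 3-point decrease in the SES-CD from baseline to the SES-CD score obtained between Week 16 and Week 17". Appendix 2 puts Items 1 and 2 into the CDAI total, with the 7-day sums multiplied by 2 and 5.

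Section 1.6 reports that the stool cut-point of 10 was picked in Phase 2 data for its balance of sensitivity, specificity and accuracy against CDAI below 150, which was taken as the gold standard. The same section says that in the Phase 3 studies "these endpoints will be evaluated for responsiveness (i.e., demonstrate the ability to detect clinically meaningful change in disease activity indexes of CD", with full CDAI as the example. It promises validity separately, as correlation with other measures of disease activity.

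Section 8.6.2 gives its own aim: "To determine whether the declaration of response based on the co-primary endpoints for induction parallels the pattern of CDAI scores". It then sets out a correlation: "Spearman correlation analyses will be applied to CDAI scores with the occurrence or non-occurrence of response". A group comparison follows: "Wilcoxon rank-sum test will be conducted to compare changes in the CDAI scores between responders and non-responders". Neither removes the shared items. The text does not say whether a responder is judged on each co-primary separately or on both together.

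**The concern.** An index correlates with its own components. Symptom remission is cut from two CDAI items, with one threshold tuned to CDAI, and is then tested against the total that contains both items. Part of any association is arithmetic, and a p-value against zero cannot separate that part from real information about the rest of the disease.

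What is at stake is interpretation. These are the only analyses described in the protocol that relate response status to another activity measure. A significant result could be presented as meeting the validity promise of Section 1.6 when it would have appeared anyway. The primary test, error control and sample size are not touched.

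**Working it through.** The protocol gives no figure for this analysis, so there is none to reproduce. Two checks apply.

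**1. Arithmetic from the protocol.** Inputs are the response thresholds (2.2.1), the weights (Appendix 2) and inclusion criterion 4 (4.1: average daily pain above 1.5 and average daily liquid or very soft stools above 1.5).

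- Most that a symptom responder can score on Items 1 and 2: 10 × 2 + 7 × 1 × 5 = 20 + 35 = 55 points.
- Weekly equivalent of the entry criterion: 7 × 1.5 = 10.5 for each item, so more than 10.5 × 2 + 10.5 × 5 = 21 + 52.5 = 73.5 points.
- Implied fall on the shared items for every responder: more than 73.5 - 55 = 18.5 points, whatever the other six items do.

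The entry averages are taken over the Screening Period, so the week used for baseline CDAI need not match them exactly. Nor is the ordering fixed for each patient. Someone with no liquid stools and one day of pain rated 2 (other days 0) is a non-responder with 0 × 2 + 2 × 5 = 10 shared points, well below 55. Responders score lower on average, not one by one.

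**2. Simulation with no true link beyond the shared items.** Items 1 and 2 were generated as daily diaries. The sum of the other six items was drawn independently of them. Its SD is not in the documents and was assumed at 30, 50, 70 or 100 points. Total sample size was 480 to 660, and symptom response rates ran from about 17% to 60%.

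| Response | Compared with | Mean Spearman | Trials with p < 0.05 |
|---|---|---|---|
| Symptom remission | Full CDAI | -0.19 to -0.51 | 99-100% |
| Symptom remission | CDAI without Items 1 and 2 | -0.01 to 0.01 | no link built in |
| Both co-primaries, endoscopic response unrelated (45%) | Full CDAI | -0.09 to -0.30 | 91-100% in most scenarios; 52-78% with SD 100 and a high response rate |
| Endoscopic response alone | Full CDAI | about 0 | 3-6% |

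The first two rows use the same simulated patients. Removing the shared items removes the whole correlation. The last row is at the nominal 5% level, so the artefact belongs to the symptom endpoint alone.

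The simulation addresses the Spearman analysis. For a yes/no variable, Spearman and the rank-sum test on the same score rest on the same ranks. For the Wilcoxon test on CDAI change, the fall in step 1 is the corresponding mechanism.

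**The case against.** The strongest reply is that 8.6.2 asks about agreement with the older index and does not use the word validity. For that aim full CDAI is a proper comparator, and the size of the association in new data is a fair check on a rule derived in Phase 2. This stands. Section 1.6 also discloses the dependence on CDAI openly, names full CDAI for responsiveness rather than validity, and speaks of the Phase 3 studies together. A separate SAP, not at hand, may add validity analyses.

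A reader might infer that the whole CDAI comparison is guaranteed to be positive and therefore worthless. The documents do not support that. SES-CD response shares no item with CDAI, so its correlation with CDAI is informative. If response means meeting both co-primaries, the artefact is weaker and significance is not assured.

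The simulated sizes also rest on assumptions. Full independence of the other six items is an extreme case, chosen to isolate the mechanism; it does not estimate what this trial will show.

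What the reply leaves standing is narrower: for symptom remission, the test against zero against full CDAI carries no validity evidence, and the protocol describes no other analysis that would.

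**Conclusion.** The point holds for the symptom co-primary only. Its comparison with total CDAI is part-whole, and a significant result is near-certain even when response is unrelated to the other six items: rho about -0.2 to -0.5 against full CDAI, against about 0 with Items 1 and 2 removed. The direction follows from the protocol's own definitions and weights. The sizes depend on assumed diary distributions and an assumed SD for the remaining items.

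The full-CDAI result may be reported as agreement. It should not be offered as the validity evidence promised in Section 1.6. A reader might also infer that the primary analysis is circular. It is not: the co-primary tests compare treatment groups and do not use total CDAI. This is a minor point about a supportive analysis.

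**What to change.** In Section 8.6.2:

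- Report symptom remission and endoscopic response separately in these analyses.
- For symptom remission, add the Spearman and Wilcoxon analyses against CDAI excluding Items 1 and 2, and against CRP, fecal calprotectin and SES-CD. CRP and calprotectin are scheduled at Visit 7 (6.3.2, 6.3.3), and SES-CD comes from the ileocolonoscopy between Weeks 16 and 17.
- Keep full CDAI for symptom remission as a descriptive measure of agreement.
- Retain the full-CDAI analysis for endoscopic response.

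IBDQ is not a clean comparator for symptom remission. It shares no diary entry, but it asks about bowel frequency, loose stools, cramps and abdominal pain (Appendix 5).

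The cost is a wording change and a few extra analyses of data already collected, with no new visits, samples or patients. Correlations for symptom remission will probably be smaller, but they can be interpreted.

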8.6.3 Safety Analyses

Safety evaluations will be based on the incidence, intensity and types of AEs, and changes in vital signs, clinical laboratory results, physical exam and electrocardiograms. Concomitant medication, exposure to study medication and treatment compliance will be summarized descriptively.

8.6.4 Extent of Exposure and Treatment Compliance

The number of subjects administered study drug, the duration of exposure to study drug, and compliance data will be summarized descriptively.

8.6.5 Adverse Events

Adverse events will be coded using the Medical Dictionary for Regulatory Activities (MedDRA) coding dictionary. Treatment-emergent AEs will be defined as any event with a start date occurring on or after Visit 2 (Day 1) or, if pre-existing, worsening after Visit 2 (Day 1).

The incidence of treatment-emergent AEs will be summarized by body system and MedDRA preferred term. If a subject reports the same AE more than once, then that subject will only be counted once for the summary of that AE, using the most severe intensity.

Treatment-emergent AEs will be summarized as follows:

- All treatment-emergent AEs;
- All treatment-emergent AEs by intensity;
- All treatment-emergent AEs related to study drug;
- All treatment-emergent SAEs; and
- All treatment-emergent AEs that led to premature discontinuation of study drug.

8.6.6 Clinical Laboratory Assessments

Laboratory values will be summarized at baseline and at each time point. In addition, changes from baseline to last visit will be summarized.

A summary of shifts from baseline to final evaluation will be given for each treatment group for each parameter. The normal range for each parameter will be used to create categories of low, normal, or high. Any result higher than ULN or lower than the lower limit of normal (LLN) will be categorized as high or low respectively, and any result within the lower and

upper limits of normal will be categorized as normal. The number and percentage of subjects in each treatment group in each shift category from baseline to final evaluation will be shown for each parameter.

All potentially clinically significant values for clinical laboratory tests will be assessed by the investigator. Out of range laboratory values that may be potentially clinically significant will be flagged for review.

8.6.7 Vital Signs

Vital sign measurements will be summarized at baseline and at each time point. In addition, changes from baseline to last visit in vital sign measurements will be summarized. For each summary the number, mean, median, standard deviation, minimum, and maximum values will be presented by treatment and study phase.

8.6.8 Concomitant Medications

Concomitant medications taken from screening and during the study will be categorized by World Health Organization (WHO) classification for therapeutic class and drug name and summarized by number and percentage of subjects.

